2.2.6.2 VISIT WINDOWS

- Pre-implantation windows vary from 2 to 30 days.
- Post-implantation imaging no sooner than 3 days post implantation and sufficiently prior to planning to allow time for image processing.
- IMRT planning must occur after imaging and no later than 21 days post marking.
- IMRT treatments must begin no more than 24 days after marking/ implantation.
- Weekly data recording has no window.
- Follow-up at the 6 months window is ± 2 weeks.
- Follow-up for all subsequent visits is ± 4 weeks.

2.2.6.3 **CTs**

CT will be taken for the *Balloon Group* up to 30 days pre-implantation, post-implantation, at the last XRT visit and at the 6-month F/U visit. Additionally, CT may be taken in the Balloon Group at 12 months if remnants of the balloon remain at 6 months.

A CT will be taken in the *Control Group* post-implantation.

Group	Up to 30 Days Pre-Implantation	Post- Implantation	Last X-RT	6 Mo	12 Mo (if needed)
Balloon	Х	Х	Х	Х	X
Control		Х			

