2.3.4.3 PRIMARY EFFICACY ANALYSES

The primary effectiveness endpoint is assessed only for subjects who receive the balloon device. The primary effectiveness endpoint is a binary assessment of whether a subject obtains at least a 25% reduction in the volume of the rectum receiving greater than or equal to 70 Gy (V_{Rectum} 70). If we denote v_e to be the percentage of subjects meeting the V_{Rectum} 70 success criteria in the balloon arm, the primary hypothesis is as follows:

H₀:
$$v_e \le 75.0\%$$
 vs H₁: $v_e > 75.0\%$

This analysis will be completed using a one-sided 0.025 exact binomial test with subjects who participate in the primary safety endpoint analysis. The exact 95% CI for the success rate will be provided as well.

Sensitivity analyses will include a tipping point analysis. To assess the validity of pooling the results across the study sites, a Likelihood Ratio chi-square test will be used to assess the homogeneity across the study sites. A p-value of greater than 0.15 will be considered supportive of pooling of the study sites.

Results will also be summarized by age greater than or equal to 65 years versus less than 65 years, and race. A likelihood ratio chi-square test will be used to evaluate the null hypothesis the factors are not associated with outcome.

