This study has co-primary endpoints for safety and efficacy. The primary safety endpoint is the rate of Grade 1 or greater rectal adverse events lasting at least 2 days through the first 183 days (six months) that are device-related or marking/implantation procedure-related. The primary efficacy endpoint will be evaluated with a one-sided test of non-inferiority using the Farrington-Manning method with a non-inferiority bound of 15%. If  $s_{pr}$  denotes the safety event rate in the *ProSpace Group* and  $s_c$  denotes the safety event rate in the *Control Group*, the primary safety hypothesis is as follows:

$$H_0: s_{pr} - s_c \ge 0.15$$
 vs  $H_1: s_{pr} - s_c < 0.15$ 

The primary efficacy endpoint is a binary assessment of whether a subject obtains at least a 25% reduction at 21 days post-implantation in the volume of the rectum receiving greater than or equal to 70 Gy ( $V_{Rectum}$  70). The primary efficacy endpoint will be assessed only for subjects who are randomized to the ProSpace Group and receive the ProSpace device, and it will be evaluated using a one-sided 0.025 exact binomial test. If we denote ve to be the percentage of subjects meeting the VRectum 70 success criteria in the *ProSpace Group*, the primary hypothesis is as follows:

$$H_0: v_e \le 75.0\%$$
 vs  $H_1: v_e > 75.0\%$ 

The hypothesis tests for the two co-primary endpoints will be considered independently without adjustment for multiplicity since both tests must reach significance for the study to successfully support the clearance of the ProSpace device. The study will be successful if both the primary safety endpoint and primary efficacy endpoint both reach statistical significance in the tests outlined above against one-sided p-value cut-offs of 0.025.

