### 10.3.4.2 Co-Primary Efficacy Endpoint and Analysis

### **10.3.4.2.1 Primary Efficacy Endpoint**

The primary efficacy endpoint is a binary assessment of whether a subject obtains at least a 25% reduction at 21 days post-implantation in the volume of the rectum receiving greater than or equal to 70 Gy ( $V_{Rectum}$  70). The primary efficacy endpoint will be assessed only for subjects who are randomized to the *ProSpace Group* and receive the ProSpace device.

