## **10.3.4.2.5 Subgroup Analyses for Primary Efficacy Endpoint**

The impact of different covariates on the primary safety outcome will be evaluated. The following covariates will be examined:

- Age, divided into two age groups of less than 65 years and greater than or equal to 65.
- Race

If the primary efficacy endpoint is found to be significantly dependent on any baseline factor, that factor will also be tested as a covariate.

Covariate analyses for the primary safety endpoint will be done using a logistic regression. Testing will focus on the covariate by treatment interaction to assess whether safety is dependent on covariate levels. In addition, descriptive statistics by covariate level will be presented.

Each covariate will be evaluated separately.

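### The SAP's efficacy subgroup section repeats the safety text, and the covariate-by-treatment interaction it specifies cannot be estimated for V70, which is scored in one arm only

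*SAP*

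**What the plan says.** SAP 10.3.4.2.5 is headed as the subgroup section for the primary efficacy endpoint. Three of its sentences concern safety instead:

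- Purpose: "The impact of different covariates on the primary safety outcome will be evaluated."
- Model: "Covariate analyses for the primary safety endpoint will be done using a logistic regression."
- Test: "Testing will focus on the covariate by treatment interaction to assess whether safety is dependent on covariate levels."

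The last sentence also stands, word for word, in SAP 10.3.4.1.5, the safety subgroup section, where both arms contribute data. SAP 10.3.4.2.5 goes on to plan descriptive summaries at each covariate level, takes covariates one at a time, and adds that other baseline factors will be tested if efficacy is found to depend on them.

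Both documents restrict V70 to one arm. SAP section 5 says: "The primary efficacy endpoint will be assessed only for subjects who are randomized to the ProSpace Group and receive the ProSpace device." Protocol 2.3.4.3 says: "The primary effectiveness endpoint is assessed only for subjects who receive the balloon device." For V70 by age and race, Protocol 2.3.4.3 plans summaries and a test suited to one arm: "A likelihood ratio chi-square test will be used to evaluate the null hypothesis the factors are not associated with outcome."

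**The concern.** An interaction with treatment asks whether the treatment contrast differs between covariate levels. V70 success has no treatment contrast, so the stated test has nothing to estimate. If the analyst instead follows the words and uses safety data, the output is the safety subgroup analysis again under an efficacy heading.

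Either way, the SAP lacks a test of whether V70 success varies with age or race. Its output list nevertheless includes Table 14.2.1.3, which reports V70 covariate analyses in the ProSpace per-protocol population. Whoever fills that table must choose a method that the SAP does not give. At stake is the pre-specification of a supportive subgroup analysis. The success criterion is not involved.

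**Working it through.** **1. The plan's own figure.** The subgroup section states no number. The figure attached to V70 is the power in Protocol 2.3.4.4.1: n = 136 evaluable balloon subjects, null rate 0.75, assumed rate 0.875, one-sided alpha 0.025, power at least 95%. The smallest r with P(X ≥ r | 136, 0.75) ≤ 0.025 is r = 113. It gives an exact alpha of 0.0159 and power P(X ≥ 113 | 136, 0.875) = 0.949. This reproduces the stated figure to rounding. No covariate or treatment term enters the calculation, so the subgroup wording cannot alter it.

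**2. Who has a V70 outcome.** Only implanted balloon subjects (SAP sections 5 and 10.3.4.2.1; Protocol 2.3.4.3). Controls could not be added. Success is a change from the pre-implantation value, and the CT schedule in Protocol 2.2.6.3 gives controls no pre-implantation scan: "A CT will be taken in the *Control Group* post-implantation."

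**3. The stated model applied to V70.** Let T be treatment and A the age group (0 or 1):

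logit P(success) = b0 + b1·T + b2·A + b3·T·A

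With T = 1 for every subject this becomes

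logit P(success) = (b0 + b1) + (b2 + b3)·A

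Only the two sums can be estimated. The design matrix [1, T, A, T·A] has 4 columns; its computed rank with 136 one-arm subjects is 2. The interaction b3 cannot be separated from b2. For race with k levels present there are 2k columns and rank k. More subjects do not help. Changing the word safety to efficacy does not help either, because T stays constant.

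**4. What one arm does support.** The model with intercept and age group has 2 columns and rank 2, so the main effect is estimable. To check that its likelihood ratio test agrees with the protocol's chi-square, take assumed counts, for illustration only: 24 of 30 successes under 65 and 95 of 106 at 65 or over (119/136 = 87.5% overall).

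- Expected successes: 30 × 0.875 = 26.25 and 106 × 0.875 = 92.75. Expected failures: 3.75 and 13.25.
- G = 2 Σ O·ln(O/E) = 2 × [24 ln(24/26.25) + 6 ln(6/3.75) + 95 ln(95/92.75) + 11 ln(11/13.25)] = 1.80 on 1 df, p = 0.18.
- The logistic regression likelihood ratio test on the same counts also gives 1.80, p = 0.18.

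**5. The related sections side by side.**

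| Section | Outcome named | Term tested | Computable for that purpose? |
|---|---|---|---|
| SAP 10.3.4.1.5 | Safety, two arms | Covariate × treatment | Yes |
| SAP 10.3.4.2.4 (efficacy poolability) | V70 success, balloon arm | Location main effect, adjusted for baseline V70 | Yes |
| SAP 10.3.4.2.5 | Safety, under an efficacy heading | Covariate × treatment | Not for V70; on safety data it repeats 10.3.4.1.5 |
| Protocol 2.3.4.3 | V70 success, balloon arm | Factor against outcome | Yes |

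SAP 3.2 lists changes to the safety window and its Kaplan-Meier analysis, the adjudication, the EPIC domains and the paired test for secondary efficacy. It lists nothing about V70 by age or race.

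**The case against.** The best defence is that this is copied text whose intent can be recovered. SAP 10.3.4.2.4 has the same slip: it speaks of safety data, then specifies a sound model with the efficacy endpoint as the dependent variable and no treatment term. Table 14.2.1.3 fixes the outcome and population. The protocol is listed among the SAP's applicable documents. No decision rule or labeling claim depends on these subgroup results. All of that stands, and it keeps the point minor. It does not remove it, because correcting the outcome alone still leaves a test that cannot be run.

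A reader might infer three stronger things, which the documents do not support:

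- *That the V70 analyses by age and race cannot be done at all.* Only the interaction test cannot. The summaries by level in the same SAP section and the protocol's chi-square test are both computable.
- *That the SAP deliberately replaced the protocol's test.* The absence of an entry in SAP 3.2 fits an intention to change nothing at least as well. What can be said is that the SAP fails to restate the test.
- *That the trigger for further factors is circular.* It can be read as extending the list beyond age and race after some screen. The screen is not described, so the sentence is unclear, but not plainly circular.

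**Conclusion.** The point holds in limited form. As written, SAP 10.3.4.2.5 specifies the wrong outcome and, for V70, a test with zero estimable degrees of freedom for either named covariate. The SAP is left without a usable inferential test of V70 success by age or race, although the protocol has one. This rests on V70 being scored only in implanted balloon subjects, which both documents state, and on no other assumption; the counts in the illustration carry no weight in it. The primary exact binomial test, its one-sided 0.025 alpha, its power, the sample size and the success rule are all unaffected. It is a minor correction, but a real one: the stated analysis is wrong, not merely short of detail.

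**What to change.** Replace the purpose, model and test sentences of SAP 10.3.4.2.5 with wording such as:

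*In the ProSpace per-protocol population, V70 success will be modelled by logistic regression on age group (under 65, 65 or over) and, separately, on race. Each main effect will be assessed by a likelihood ratio test, equivalent to the test in Protocol 2.3.4.3. Success rates by level will be reported in Table 14.2.1.3.*

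Remove the treatment interaction and every reference to safety from the section. Clarify the sentence on other baseline factors by stating which factors are considered and how dependence is first judged; it need not be deleted. Exact confidence intervals by level are optional. Since this restores the protocol's test, it needs no new data and no change to the protocol, sample size or primary analysis. The cost is a wording change to the SAP.

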#### **10.3.5** Secondary Endpoints and Analyses

Secondary analyses will be done using the PP population.

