2.3.2 ANALYSIS POPULATIONS

The intent-to-treat (ITT) population consists of all subjects randomized for the study. The primary analysis population will be based on a Per-Protocol population consisting of ITT in the Control Group and subjects who were randomized to the balloon Group. The ITT population analysis will be included in a sensitivity analysis.

The primary analyses will be completed using a Per-Protocol (PP) Population consisting of subjects who were randomized to and received the balloon device or were randomized to the *Control Group*. It is anticipated that there may be one or two subjects that get randomized to the balloon device, but are not implanted. These subjects will not be included in the PP population or be required to be followed per the protocol. However, the subjects will be included as failures in a sensitivity analysis in the primary analyses for the study.

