#### Intent-to-Treat (ITT) Population

Intent-to-Treat (ITT) population will include all randomized subjects, regardless of whether they underwent a surgery or not. All subjects in the ITT population will be analyzed as members of the group to which they were assigned irrespective of actual treatment received.

The ITT population will be used for a sensitivity analysis for the study co-primary endpoints.

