#### Per-Protocol (PP) Population

The Per-protocol (PP) population is a subset of the ITT population, and will include:

- All subjects randomized to the Control group.
- *ProSpace* group subjects who were marked and implanted as planned.

The PP population will be used for analyses of the study's primary and secondary endpoints (efficacy and safety).

A listing of all protocol deviations will be evaluated prior to the database lock by the study's medical monitor (clinical expert).

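### The labelling superiority tests are planned only in a Per-Protocol set that drops non-implanted men from the balloon arm alone, so a borderline claim could depend on who was left out

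*SAP*

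**What the plan says.** SAP 10.2 opens the labelling tests once both co-primary endpoints have succeeded, describes them as secondary, and sets 0.0167 two-sided for each. It announces three but lists two: Fisher's exact tests on the primary safety endpoint and on the Grade 2 or greater rectal event rate. The third, a rank-sum test on EPIC, is named only in Protocol 2.3.3.

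The population is fixed in two places. SAP 10.3.5: "Secondary analyses will be done using the PP population". SAP section 9: "The PP population will be used for analyses of the study's primary and secondary endpoints (efficacy and safety"). Section 9 builds that population differently in the two arms. Controls: "All subjects randomized to the Control group". Balloon arm: only "group subjects who were marked and implanted as planned".

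The intent-to-treat set has a narrower role: "The ITT population will be used for a sensitivity analysis for the study co-primary endpoints". Protocol 2.3.2 covers the men who are left out. It forecasts their number ("It is anticipated that there may be one or two subjects that get randomized to the balloon device, but are not implanted"), does not ask for their data ("These subjects will not be included in the PP population or be required to be followed per the protocol"), and counts them as failures for the primary analyses only ("However, the subjects will be included as failures in a sensitivity analysis in the primary analyses for the study").

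**The concern.** A labelling claim of superiority over a randomised control should rest on the groups as randomised. Here balloon men can leave the comparison after randomisation and control men cannot leave by the same route: inability to dissect is an intra-operative exclusion for the balloon arm only (Protocol 2.2.3.2). A man whose implantation is attempted and abandoned can still have a qualifying event. Protocol 2.3.6.1 lists rectal wall puncture among the marking and implantation risks, and SAP 10.3.4.1.1 counts events related to marking or to the implantation procedure. His event would be missing from the test used to claim that the balloon arm has fewer such events.

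The plan protects the co-primaries against this with intent-to-treat and failure-rule analyses, but gives the labelling tests no equivalent. Because non-implanted men need not be followed, the data for a later as-randomised test may not exist.

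**Working it through.** **1. The plan's own figures.**
- Level per labelling test: 0.05/3 = 0.0167. Reproduces. The half that favours the balloon is 0.0167/2 = 0.83%.
- Enrolment: 204/0.92 = 221.7, rounded up to 222; at 2:1 this is 148 balloon and 74 control. Reproduces.
- Safety non-inferiority power (19% v 21%, margin 15%, 136 v 68, one-sided 0.025). The Farrington-Manning null rates are 27.17% and 12.17%. Null SE = √(0.2717×0.7283/136 + 0.1217×0.8783/68) = 0.0550. Alternative SE = √(0.19×0.81/136 + 0.21×0.79/68) = 0.0598. Power = Φ[(0.17 − 1.96×0.0550)/0.0598] = 85.1%, against 85% stated. Reproduces.

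The point therefore concerns the analysis population. The design arithmetic is not in question.

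**2. Is there an as-randomised safeguard elsewhere?**

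| Place | What it covers | Protects the superiority tests? |
|---|---|---|
| SAP 9, ITT | sensitivity analysis of the co-primaries | No |
| Protocol 2.3.2, failure rule | primary analyses | No |
| SAP 10.3.4.1.3, ITT tipping point | the primary safety hypothesis, which SAP 10.3.4.1.2 defines as non-inferiority | No |
| SAP 12, tables | Grade 2 and EPIC analyses in Per-Protocol only | No |
| Protocol 2.2.5.1 | ITT analysis of all enrolled, but men removed before implantation are excluded from analysis | No |

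**3. Can one or two men change a result?** Two-sided Fisher's exact test, threshold 0.05/3. The counts are assumed. The first pair takes a control count near the protocol's 21% (0.21×74 = 15.5, taken as 16) and the largest balloon count that still wins in Per-Protocol. The others stand for the Grade 2 endpoint, for which the documents give no rate.

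| Per-Protocol | p | Excluded men restored | p |
|---|---|---|---|
| 13/147 v 16/74 | 0.0110 | one, with event: 14/148 | 0.0205 |
| 13/146 v 16/74 | 0.0113 | two, both with events: 15/148 | 0.0245 |
| 3/136 v 8/68 | 0.0073 | one, with event: 4/137 | 0.0221 |
| 3/136 v 8/68 | 0.0073 | one, **no** event: 3/137 | 0.0070 |
| 3/136 v 10/68 | 0.0012 | two, both with events: 5/138 | 0.0079 |

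The first three rows lose the claim. The fourth strengthens slightly. The fifth keeps the claim.

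**4. How often does a claim reverse?** Assume Grade 2 rates of 3% v 12% with 136 v 68. Enumerating both binomials, Per-Protocol claims superiority 47% of the time. Adding one balloon event reverses about 17% of those claims, and adding two reverses about 34%.

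**5. False favourable claims.** Assume both arms truly have 21% as randomised (148 v 74) and that all k non-implanted men have events. The implanted men then have rate (0.21×148 − k)/(148 − k).

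| k | Rate in implanted men | False claim, Per-Protocol | False claim, as randomised |
|---|---|---|---|
| 0 | 21.0% | 0.69% | 0.69% |
| 1 | 20.5% | 0.85% | 0.67% |
| 2 | 19.9% | 1.17% | 0.64% |
| 5 | 18.2% | 2.55% | 0.56% |

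At k = 5 the Per-Protocol rate is about three times the nominal 0.83% (2.55/0.83 = 3.1).

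**The case against.** The case against a strong reading is good, and most of it stands.

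- **Direction.** A reader might infer that the exclusion always favours the balloon. It does so only if the excluded man has a qualifying event. Removing an event-free man slightly raises the balloon rate, and restoring him can even help: 5/136 v 9/68 gives p = 0.01696 (no claim) and 5/137 gives p = 0.01657 (claim). A man who never receives the device also cannot qualify through device-relatedness.
- **Reasons for exclusion.** A reader might infer that these men are left out because the procedure injured them. The stated reasons are a health concern that arises (Protocol 2.2.3), inability to dissect (2.2.3.2), and an adverse event that prevents or delays radiotherapy (2.2.5.1). Some men never reach the procedure. Events after an abandoned attempt are possible, but the documents do not give injury as the reason for exclusion.
- **Size.** A reader might infer that one or two men are enough to overturn any claim. The counts above are assumed, they sit near the threshold, and the reversals give every restored man an event. Clearer results survive. Protocol 2.2.5.1 expects very few intra-operative exclusions, if any.
- **Existing visibility.** Adverse event listings are on the intent-to-treat set (SAP 12), so recorded events in these men are not hidden. One or two men among 148 should hardly move a rank-sum test on EPIC.
- **Remedy.** It is tempting to count every non-implanted balloon man without follow-up as an event. Since follow-up of these men is not required, that would assign events to nearly all of them, in one arm only, while SAP 10.3.4.1.1 drops controls lost before Day 169. One asymmetry would replace another.

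What remains is that no as-randomised version of any labelling test is planned, and listings do not supply one.

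**Conclusion.** The point holds in limited form. As written, a superiority claim for labelling would come from a comparison that omits some men from one arm after randomisation, with no planned analysis of the superiority hypothesis as randomised. The bias favours the balloon when the omitted men have qualifying events.

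At the one or two men the protocol expects, it matters only for a borderline result: p moves from 0.011 to between 0.021 and 0.025, or from 0.007 to 0.022. Even in the worst case the false-claim rate is 0.85% to 1.17%, against a nominal 0.83%. It becomes material at about five men (5/148 = 3.4%), which the documents do not forecast. These figures rest on assumed event counts and on every excluded man having an event. The reading that non-implanted men are the ones removed rests on Protocol 2.3.2; SAP 9 does not define what implanted as planned means.

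This should be corrected, but it does not threaten the co-primary analyses, which have their own sensitivity analyses.

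**What to change.** 1. **SAP 10.2 and 10.3.5:** state that the labelling superiority tests use all randomised men in their assigned groups, counting events observed in non-implanted men, with the Per-Protocol result shown as supportive. EPIC uses all randomised men with data.
2. **Protocol 2.3.2:** amend so that adverse events and EPIC are collected to 6 months for non-implanted men who consent.
3. **Incomplete follow-up:** treat men in either arm who have no event and are not followed to Day 169 by one common rule, and add a tipping-point analysis scored on the superiority test.
4. **Worst case only:** show the count that treats every non-implanted balloon man as an event as a sensitivity analysis, and label it as an extension of the protocol's failure rule.

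The cost is a protocol amendment, a few sentences in the SAP, re-runs of existing programs, and follow-up of a few men. The claim may come out slightly less favourable. If the follow-up cannot be added, items 1, 3 and 4 can still be done with the data recorded.
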